6.4. Visit Windows

All data collected during study follow-up will be displayed and analyzed according to the actual visit data in the eCRF with the exception of early termination visits. Early termination visits will be mapped to the closest study visit, or analyzed according to the actual visit date, when possible.

The study assessments are summarized in Table 1 and Table 2 of the clinical study protocol. All information required by the protocol must be recorded on the source documents. The study schedule must be followed. However, under special conditions (e.g., holidays, weekends), a window of +/- 3 days is permissible for study procedures as long as the proper order of procedures and assessments is maintained. In Phase 2, a window of +/- 7 days is permissible. These windows are not applicable during the baseline period. Out-of-window data will be retained in the tables, listings, and figures. For the Part A interim analysis, Visit 8 will include data collected up to 36 weeks for HRCT and 28 weeks for all other variables.

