The DSMB for this study met on 12 OCT 2020 to review preliminary dose comparison data. It was determined that the 100 mg twice daily dose showed a trend for amelioration of FVC loss and recommended all patients in Part B be treated with the 100 mg twice daily dose. Therefore, all patients who participate in Part B after the implementation of this amendment will be treated with the 100 mg twice daily dose. Any patients already participating in Part B on the 50 mg once daily dose will be converted to the 100 mg twice daily dose regimen. Patients will have monthly telephone assessments and quarterly in-clinic assessments. All patients that complete the study visits through Part B will have the option to continue receiving AP01 by enrolling or planning to enroll in the AP01-005 study or to stop dosing after the EOS/Visit 12 and return for a Follow-up visit, 28 days after their End of Study visit.

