## 5.3. Study Restrictions

Patients are not to receive pirfenidone or nintedanib within 3 days prior to randomization to the study and during participation in Part A of the study. Nintedanib, but not oral pirfenidone, use is allowed if deemed necessary by the investigator during Part B of the study. In the event of an acute exacerbation, any treatment deemed necessary by the investigator is acceptable until the resolution of the event. Other than brief periods of medically appropriate treatment for acute IPF exacerbation, patients will not receive any other therapy for the treatment of IPF during Part A. If in the opinion of the investigator, a patient is in need of treatment with oral pirfenidone or nintedanib during Part A, the patient should be discontinued from the study and return to the clinic for their Early Termination visit. Oxygen use is allowed during the study.

Avalyn Pharma, Inc.  
AP01-002

Protocol v2.1  

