#### **6.2.6. Visit 8 - End of Part A (Day 168 +/- 3 days)**

The following procedures will be conducted at the listed visits in chronological order:

- Cough VAS, KBILD Questionnaire and LCQ
- AEs and concomitant medications since previous visit
- Modified PE (Lungs and CV body systems only)
- Weight
- Vital signs
- SaO2
- Spirometry and DLCO
- Blood samples for laboratory tests (Chemistry including AST and ALT, Hematology, Biomarkers (CA19-9 and CA-125 only))
- Urinalysis
- Urinary pregnancy test (FOCBP only)
- HRCT
- LCM dispensation
- End of Treatment form for Part A completion
- Study material dispensation (3-month supply for patients participating in Part B only)

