### **7.3.2. Extent of fibrosis and lung volumes as assessed by HRCT**

HRCT scans will be obtained to measure the extent of fibrosis and lung volumes at Baseline and the Week 24 visits. These scans will be read and interpreted by a central reader.

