8.1. Primary Efficacy Endpoint and Analysis

Spirometry will be conducted at approximately the same time each visit (within 60 minutes of Day 1 spirometry measurement) with the patient in seated position. The test will be performed to American Thoracic Society/European Respiratory Society (ATS/ERS) guidelines³. On days of clinic visits (including the screening visit), patients must refrain from strenuous activity at least 12 hours prior to pulmonary function testing (PFT). FVC % predicted will be calculated using the ERS Global Lung Function Initiative 2012 equations² as outlined in the clinical study manual.

PFTs will be collected at Screening, Baseline and at each post-Baseline time point (Week 4, 8, 12, 16, 20, 24, 36, 48, 60, 72 and Follow-Up) as described in Section 6.1.

The primary efficacy endpoint is the change from baseline in absolute FVC % predicted from Baseline to Week 24. The population used for efficacy analyses of the primary variable will be the PP with the FAS used for the first sensitivity analyses.

A linear mixed-effects model (PROC MIXED) will be used and differences between treatment groups between slopes estimating the change from baseline in absolute FVC % predicted from Baseline to Week 24 will be examined. Baseline FVC % predicted, region, age at screening, sex, baseline DL_{CO} % predicted, and baseline progression-related biomarker (CXCL13, CCL18, MMP3) values each categorized as >Median level vs. ≤Median level will be included as covariates in the model. This analysis requires at least three post-baseline FVC % predicted values in addition to baseline be available for a patient to be included in the analysis so that the slope estimated is identifiable. Similar modeling strategies will be employed for longer-term data obtained from Part B of the study. Spirometry data collected after patients switched dosing regimen from 50 mg once daily to 100 mg twice daily will be omitted for this analysis.

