The following plot will be produced for extent of fibrosis and lung volumes as assessment by HCRT:

This document is confidential.

SAP Version: 3.0 (15JUL2021)
Controlled Document ID: **3903A.01**, Effective Date 29-Oct-2018
Filing requirements: TMF

Page 35 of 52

Statistical Analysis PlanSponsor: Avalyn Pharma, Inc.; Protocol No.: AP01-002

- Mean Extent of Fibrosis (or Lung Volume) Change from Baseline (\pm SD) vs. Weeks from Baseline (calculated based on visit date) for each lung region with lines for each treatment group.

A linear model will be used and differences between treatment groups between the change from baseline in whole lung extent of fibrosis and whole lung volume from Baseline to post-Baseline will be examined. Change from baseline will be the dependent variable and baseline whole lung extent of fibrosis (or whole lung volume), region, age at screening, sex, baseline D_{LCO} % predicted and baseline progression-related biomarker (CXCL13, CCL18, MMP3) values each categorized as $>$ Median level vs. \leq Median level, and time of HRCT (relative to baseline) will be included as covariates in the model.

All HRCT scan data will be presented in a listing including early termination and unscheduled visits.

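### HRCT scans taken after a 50 mg patient switched to 100 mg twice daily can enter the dose comparison as 50 mg data, because SAP 6.4, 8.2.5 and 9.3 give no switch rule for HRCT

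*SAP*

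**What the plan says.** Protocol 7.3.2 plans only two scans: "HRCT scans will be obtained to measure the extent of fibrosis and lung volumes at Baseline and the Week 24 visits". Protocol 6.2.6 puts Visit 8 at Day 168 with a margin of 3 days either way. SAP 6.4 is much wider. For the Part A interim analysis, "Visit 8 will include data collected up to 36 weeks for HRCT and 28 weeks for all other variables". The same section says generally that "Out-of-window data will be retained in the tables, listings, and figures", and it sets no upper limit for HRCT in the final analysis.

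Treatment can change once a patient is in Part B. The protocol synopsis (Study Overview/Design) says that "Any patients already participating in Part B on the 50 mg once daily dose will be converted to the 100 mg twice daily dose regimen", and patients entering Part B after the amendment is implemented receive 100 mg twice daily. Protocol 5.3 adds: "Nintedanib, but not oral pirfenidone, use is allowed if deemed necessary by the investigator during Part B of the study".

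SAP 8.2.5 compares change in whole-lung fibrosis and lung volume between arms in a linear model, in which "time of HRCT (relative to baseline) will be included as covariates in the model". SAP 9.3 relates HRCT measures to FVC with treatment group in the model. Neither section mentions the switch.

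Other sections do. For the primary FVC slope (SAP 8.1), "Spirometry data collected after patients switched dosing regimen from 50 mg once daily to 100 mg twice daily will be omitted for this analysis". The correlation and home-spirometry analyses in 9.1, 9.2 and 9.4 also omit post-switch data or use only pre-switch data. The all-visit FVC model (8.1), the DLCO model (8.2.6) and the biomarker model (9.4) use time-varying treatment.

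**The concern.** A 50 mg patient whose Week 24 scan is delayed until after the switch has a scan that reflects some time on 100 mg twice daily, yet it is analysed as 50 mg. The scan-time covariate adjusts for when the scan was taken, not for which regimen the patient was on.

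SAP version 3.0 is dated 15 JUL 2021, after the DSMB meeting of 12 OCT 2020, and it handles the switch for FVC, DLCO, home spirometry and biomarkers. The silence on HRCT therefore looks like an omission. Delayed scans are plausible, since Protocol 11.2.3 says that the pandemic occurred during enrolment.

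What is at stake is estimation. Estimating each regimen's effect on HRCT, and comparing the two regimens to guide later studies, are stated objectives (Protocol 2; SAP 3.2). No formal HRCT test is planned, so type I error is not the issue.

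**Working it through.** The documents give no sample size, power or effect size for HRCT, so there is no planned figure to reproduce.

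**Window.** Week 36 is Day 36 × 7 = 252. The last in-window day for Visit 8 is 168 + 3 = 171. The interim allowance runs 252 − 171 = 81 days past the protocol window, and 36 − 24 = 12 weeks into Part B.

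**Who can be affected.** No switch under this amendment can precede 12 OCT 2020. First dose is study day 1 (SAP 6.2.5), so Day 252 falls on 12 OCT 2020 for a first dose 251 days earlier, on 4 FEB 2020. In the interim analysis, patients first dosed before about that date cannot have a post-switch scan inside the window. The final analysis has no HRCT limit, so only the scan date relative to the switch matters there.

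**Effect on the contrast.** Let *a* and *b* be the weekly change on 100 mg and 50 mg. Assume that a fraction *f* of each arm is scanned late, uniformly over Weeks 24 to 36, and the rest at Week 24. The mean scan time is then 24 + 6*f* weeks. Scan times are distributed alike in both arms, so in a model with treatment and scan time the treatment coefficient equals the difference in arm means. The other covariates of 8.2.5 are left out.

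1. Linear progression, late 50 mg patients switched at Week 24. At scan time *t*, a 100 mg patient has changed by *ta* and a switched patient by 24*b* + (*t* − 24)*a*. The difference is 24(*a* − *b*) at every *t*, which is the Week 24 contrast.
2. Immediate full effect, with a switched patient taking the 100 mg mean at once. The difference is (1 − *f*) times the Week 24 contrast.
3. Linear progression, late but not switched. The difference is (24 + 6*f*)(*a* − *b*), or (1 + *f*/4) times the Week 24 contrast.

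With the true Week 24 difference set to 2.0 arbitrary units:

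| Assumed *f* | 1. Linear, switched | 2. Immediate effect | 3. Linear, not switched |
|---|---|---|---|
| 10% | 2.00 | 1.80 | 2.05 |
| 30% | 2.00 | 1.40 | 2.15 |
| 50% | 2.00 | 1.00 | 2.25 |

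A least-squares simulation of this model gave the same values to two decimals. The documents do not give *f*; these values are assumptions.

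**Effect of a switch-date rule.** Drop the post-switch scans in scenarios 1 and 2. Every remaining 50 mg scan is at Week 24, the scan-time coefficient is estimated from the 100 mg arm, and the treatment coefficient returns to 2.0 in both.

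**Precision cost.** With 50 patients per arm (Protocol 11.1) and a fraction *f* of the 50 mg arm removed, the standard error grows by √{[1/50 + 1/(50(1 − *f*))] / (2/50)} = √{[1 + 1/(1 − *f*)]/2}. That is 1.03, 1.10 and 1.22 at 10%, 30% and 50%, ignoring covariates, dropout and the new imbalance in scan time.

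**The case against.** - **Analysis as randomised is declared** (Protocol 11.2; SAP 5.2 and 5.3). This stands as a legitimate estimand, and it is why the all-scans analysis should still be reported. But the SAP departs from it for the switch in its FVC and DLCO models and does not say that HRCT is meant to differ.
- **Exposure may be small.** Protocol 6.2.6 lists HRCT before Part B supplies are dispensed, so an on-schedule scan precedes any switch, and the calendar limit above removes more patients. This stands.
- **FVC is a weak analogy.** Dropping post-switch spirometry leaves a patient's earlier visits in the model. HRCT has one planned post-baseline scan, so dropping it removes the patient from the change model. This stands as a cost.
- **Late scans without a switch also move the estimate** (scenario 3). They reflect a later contrast, not mixed regimens. This is a limitation of keeping them.
- **Much is already visible.** Switch flags are listed, switch timing is summarised, and HRCT is plotted by actual weeks. This helps a reader but does not change the model. The five-group split in SAP 6.1 is for Part B and does not clearly reach a Visit 8 scan.
- **HRCT is not the only silent model.** The cough-monitor model in SAP 8.2.1 also lacks a switch rule, although its interim Visit 8 allowance ends at Week 28.

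A reader might also infer that scans after nintedanib start should be excluded. The documents do not support that for the main analysis. Nintedanib is permitted in Part B at the investigator's discretion in an open-label trial, so exclusion would select on a post-randomisation, judged event, possibly unequally by arm. The regimen switch was applied to Part B as a whole by amendment.

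**Conclusion.** The gap is real, and its consequence is conditional: the HRCT dose comparison can be contaminated by post-switch scans, at the interim analysis up to Week 36 and at the final analysis with no stated limit. The loss ranges from none (linear progression, switch at Week 24) to roughly the fraction of the 50 mg arm scanned post-switch (immediate full effect). The documents settle neither the time course nor that fraction.

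A reader might infer three stronger things. First, that the comparison is contaminated: the number of late or post-switch scans is not given. Second, that it is pulled toward no difference: this fails under linear progression with a Week 24 switch. Third, that the share of follow-up spent on the other regimen, at most 12 of 36 weeks, is the dilution: that share applies to a Week 36 contrast, and the planned time point is Week 24.

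HRCT is a secondary endpoint, so what is affected is estimation and dose guidance.

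**What to change.** In SAP 6.4, 8.2.5 and 9.3, for both the interim and the final analysis:

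- Restrict the main HRCT analysis to scans taken on or before the dosing switch date defined in SAP 6.2.8.
- Keep late scans from patients still on their randomised regimen, with the scan-time covariate.
- Report the all-scans, as-randomised analysis as a sensitivity analysis.
- Tabulate late, post-switch and post-nintedanib scans by arm.
- Do not exclude on nintedanib start in the main analysis; examine it in a sensitivity analysis.

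The work is SAP wording and a filter on a date that the SAP already defines, plus one table and the sensitivity runs. The statistical cost is that a patient whose only post-baseline scan is post-switch leaves the main change model, with a loss of precision that depends on how many such scans there are.

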6.5. Pooling of Centers

All centers will be pooled for summaries by treatment regimen. No by site analyses will be performed.

6.6. Subgroups

Subgroup analyses will be performed based on baseline groupings for FVC % predicted (FVC % predicted \leq 65, 65 < FVC % predicted < 80, and FVC % predicted \geq 80 at Baseline), region (Asia-Pacific and Europe), supplemental oxygen use (Y/N), age at screening categorized as >Median level vs. \leq Median level, sex, DLCO % predicted categorized as >Median level vs. \leq Median level, and progression-related biomarkers (CXCL13, CCL18, MMP3) each categorized as >Median level vs. \leq Median level provided each stratum contains at least 10 patients. Analyses of the primary efficacy endpoint will be performed by each subgroup in addition to by treatment group. In addition, a general

This document is confidential.

SAP Version: 3.0 (15JUL2021)
Controlled Document ID: **3903A.01**, Effective Date 29-Oct-2018
Filing requirements: TMF

Page 24 of 52

Statistical Analysis PlanSponsor: Avalyn Pharma, Inc.; Protocol No.: AP01-002

safety summary (overall AE summary, summary of respiratory [SOC respiratory, thoracic and mediastinal disorders] TEAEs by Preferred Term and summary of tolerability including cough due to drug administration and bronchospasm after in-clinic drug administration) will be performed by each subgroup in addition to by treatment group.

This document is confidential.

SAP Version: 3.0 (15JUL2021)
Controlled Document ID: **3903A.01**, Effective Date 29-Oct-2018
Filing requirements: TMF

Page 25 of 52

Statistical Analysis PlanSponsor: Avalyn Pharma, Inc.; Protocol No.: AP01-002

7. Demographic, Other Baseline Characteristics and Medication**7.1. Patient Disposition and Withdrawals**

The number of patients in each study population will be summarized by treatment group and overall. In addition, for each study part (Part A and Part B), patients' status with regard to study treatment and follow-up will also be summarized by treatment group and overall, along with the reasons for study discontinuations. The timing of the switch to 100 mg twice daily in Part B for 50 mg once daily patients and duration of time on 100 mg twice daily will be summarized.

All patient disposition data will be presented in a listing.

7.2. Demographic and Baseline Characteristics

Demographics and baseline characteristics (age, sex, ethnicity, race and childbearing potential (and reason, if No)) will be summarized by treatment group and overall with descriptive statistics for Part A and Part B.

All demographic and baseline characteristics data will be presented in a listing.

7.3. Medical History

Medical history will be coded according to the Medical Dictionary for Regulatory Activities (MedDRA 21.1 or higher). Medical history will be listed by treatment group, patient number, start date and end date

7.4. Other Baseline Characteristics

Other baseline characteristics will be summarized by treatment group and overall with descriptive statistics for Part A and Part B including:

- IPF Diagnosis
 - Time since diagnosis
 - IPF-related cough (All the time, Most times during the day, Several times during the day, Sometimes during the day, Occasionally through the day, Rarely, Never)
- Smoking history:
 - Smoking Status (Current smoker, former smoker, never smoked)
 - For Current or Former Smokers Only:
 - Years smoked (Current Year – Year Started +1 for Current Smoker; Year Quit – Year Started +1 for Former Smoker)
 - Cigarette pack-years
 - Patients with ≥ 20 cigarette pack-years vs. patients with < 20 cigarette pack-years.
- Region (Asia-Pacific and Europe)

This document is confidential.

Statistical Analysis PlanSponsor: Avalyn Pharma, Inc.; Protocol No.: AP01-002

- Disease Severity at Screening (40% predicted \leq FVC < 50% predicted and FVC \geq 50% predicted)
- Disease Severity at Baseline (FVC % predicted \leq 65, 65 < FVC % predicted < 80, and FVC % predicted \geq 80 at Baseline)
- FVC % predicted at Screening
- FVC (L) at Screening
- Progression related biomarkers at Baseline
 - CXCL13
 - CCL18
 - MMP3

All data for other baseline characteristics will be presented in a listing.

7.5. Drug Exposure

In this study, patients will be dosed in the clinic at Baseline to confirm tolerability for the first (and possibly second dose) and at home by the patient for all post-baseline doses. Drug exposure will be assessed as follows:

Baseline: In the Clinic

- The actual dose (mL) of AP01 for each patient will be the starting volume in the nebulizer minus the remaining volume in the nebulizer (if the full dose was not administered). If a second dose is given due to intolerance at the first dose, the actual dose will be derived in the same manner as the first dose. The number of patients who require a second dose in-clinic will be summarized and the total actual dose for each dose will be summarized by treatment group.
- The number of patients with physician-prescribed salbutamol taken prior to the dose will be summarized for each dose (first dose only if only 1 dose was received or for each dose if 2 doses are received) by treatment group with frequency counts and percentages. For patients who received salbutamol prior to dose, how many of those are because of prior toxicity for each dose and how many were added due to intolerance for the second dose will be summarized by treatment group with descriptive statistics.
- The number of patients with study drug inhalations interrupted will be summarized for each dose (first dose only if only 1 dose was received or for each dose if 2 doses are received) by treatment group with frequency counts and percentages.
- For patients with Inhalation interrupted during the second dose, the number of patients with salbutamol administered to continue dosing will be summarized by treatment group with frequency counts and percentages.
- For each patient, the time of nebulization for each dose will be derived as the study drug administration stop time minus the study drug administration start time and converted to minutes. If the study drug inhalation was interrupted, the time of interruption for each dose will be derived as the Inhalation Re-Start Time minus the Inhalation Interruption Time, converted to minutes and

This document is confidential.

SAP Version: 3.0 (15JUL2021)
Controlled Document ID: **3903A.01**, Effective Date 29-Oct-2018
Filing requirements: TMF

Page 27 of 52

Statistical Analysis PlanSponsor: Avalyn Pharma, Inc.; Protocol No.: AP01-002

then subtracted from the time of nebulization. Time of nebulization will then be summarized for each dose by treatment group with descriptive statistics. In addition, the Time of nebulation will be summarized for just those patients who took the full dose with no interruptions for each dose by treatment group with descriptive statistics.

- To assess tolerance, the number of patients with a $\geq 15\%$ drop from pre-dose FEV₁ % predicted to post-dose FEV₁ % predicted will be summarized for each dose (first dose only if only 1 dose was received or for each dose if 2 doses are received) by treatment group with frequency counts and percentages (see more details in Section 10.6).

Post-Baseline: At Home

- For each patient, the treatment days will be derived cumulatively across all visits as the last dose date minus the first dose date + 1 and will be summarized by treatment group with descriptive statistics.
- For each patient, the actual total dosage (mg) of AP01 will be derived cumulatively across all visits across all patient doses as 50 times the total number of used ampoules returned, and will be summarized by treatment group with descriptive statistics.
- For each patient, the percent compliance will be derived cumulatively across all visits across all patient doses as 100 times (the total number of used ampoules returned divided by the total number of ampoules that would be used if they were fully dosing for the number of days between visits {slightly different from the number of ampoules dispensed}). If a subject discontinues early, the denominator will be the total number of ampoules, which would be used up to, and including the date of discontinuation. Percent compliance will be summarized by treatment group with descriptive statistics. The percent compliance will be categorized ($\geq 80\%$, 60- $<80\%$, 40- $<60\%$, 20- $<40\%$ and $<20\%$) and summarized by treatment group with frequency counts and percentages. The percent compliance will be calculated overall and separately for each dosing regimen for those patients who switch over from 50 mg once daily to 100 mg twice daily in Part B.
- For each patient, the percent compliance with the patient's care plan will be derived cumulatively across all visits across all patient doses as 100 times (the total number of used ampoules returned divided by the total number of ampoules that would be used if they were fully dosing for the number of days between visits minus the number of ampoules that would be missed if following instructions to reduce or interrupt dose). If a subject discontinues early, the denominator will be the total number of ampoules, which would be used up to, and including the date of discontinuation. Percent compliance will be summarized by treatment group with descriptive statistics. The percent compliance will be categorized ($\geq 80\%$, 60- $<80\%$, 40- $<60\%$, 20- $<40\%$ and $<20\%$) and summarized by treatment group with frequency counts and percentages. The percent compliance will be calculated overall and separately for each dosing regimen for those patients who switch over from 50 mg once daily to 100 mg twice daily in Part B.
- The number of patients who had any days where all doses were missed will be summarized cumulatively across all visits by treatment group with frequency counts and percentages. For those patients who had any days where all doses were missing, the maximum number of days between doses will be summarized cumulatively across all visits by treatment group with descriptive statistics.

This document is confidential.

SAP Version: 3.0 (15JUL2021)
Controlled Document ID: **3903A.01**, Effective Date 29-Oct-2018
Filing requirements: TMF

Page 28 of 52

Statistical Analysis PlanSponsor: Avalyn Pharma, Inc.; Protocol No.: AP01-002

All recorded information for study medication administration and accountability for AP01 will be listed.

All recorded information for Nebulizer Training, Nebulizer and Nebulizer handset accountability will be listed.

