12 OCT 2020

The initial dose of drug will be administered in the clinic to confirm airway tolerance. If based on the investigator's opinion, the patient had tolerability issues during the first dose administration, a second dose, at least 4 hours later, will also be observed. Patients who experience cough that limits their ability to complete dosing will be given 1 - 2 puffs (90 - 100 micrograms ( $\mu\text{g}$ )) of salbutamol in order to complete the in-clinic dose. These patients, as well as patients with a history of asthma or smoking history of 20 pack years or greater, or patients that have a  $\geq 15\%$  drop in FEV1 percent predicted in their pre-dose and post-dose readings will be required to use 1 - 2 puffs (90 - 100  $\mu\text{g}$ ) of salbutamol prior to dosing throughout the study unless these patients are currently taking a long-acting beta-2-agonist therapy.

Patients will have a telephone assessment at Week 1 and in-clinic assessments at Weeks 4, 8, 12, 16, 20, and 24. The Data and Safety Monitoring Board (DSMB) will perform a review of safety data from the first 20 patients after Week 4 to confirm the safety and airway tolerability of multiple dose administration. A decision to stop, continue or modify the study will be made based on this review.

Part B will collect long term safety and efficacy data for an additional 48 weeks. Patients who complete Part A through Week 24 and, in the opinion of the investigator are compliant with treatment, may select to continue the treatment to which they were randomized. The DSMB for this study met on 12 OCT 2020 to review preliminary dose comparison data. It was determined that the 100 mg twice daily dose showed a trend for amelioration of FVC loss and recommended all patients in Part B be treated with the 100 mg twice daily dose. Therefore, all patients who participate in Part B after the implementation of this amendment will be treated with the 100 mg twice daily dose. Patients participating in the AP01-005 study will continue treatment that they are receiving at Visit 12 on this study and then transition to the Rollover study upon approval of AP01-005 at their site.

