### **8.6. Investigational Drug Administration**

Patients will be trained on use of the eFlow and administration of the study drug at the Baseline visit. The first dose of study drug for each patient will be administered and observed at the clinical study site at the Baseline visit to confirm tolerability. All subsequent doses will be administered by the patient at home. All doses must be taken at least 4 hours apart.

Patients who experience cough that limits their ability to complete dosing will be given 1 – 2 puffs (90 - 100 µg) of an inhaled beta 2 agonist, such as salbutamol, in order to complete the in-clinic dose. These patients, as well as patients with a history of asthma or smoking history of 20 pack years or greater, or patients that have a  $\geq 15\%$  drop in FEV1 percent predicted in their pre-dose and post-dose readings and are symptomatic will be provided with and required to use 1 - 2 puffs (90 - 100 µg) of salbutamol prior to their second dose and for dosing throughout the study, unless these patients are currently taking a long-

Avalyn Pharma, Inc.  
AP01-002

Protocol V2.1  

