3.1. Primary Objective

The primary objective is to evaluate safety and tolerability of treatment with AP01 given once or twice daily to patients with idiopathic pulmonary fibrosis (IPF) by monitoring adverse events (AEs) and post-dose spirometry.

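### SAP 7.5 counts salbutamol given to finish an interrupted inhalation only for the second in-clinic dose, so no table shows how many patients needed it to finish the first

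*SAP*

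**What the plan says.** The primary objective (SAP 3.1) is to "evaluate safety and tolerability of treatment with AP01 given once or twice daily", judged by adverse events and post-dose spirometry.

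On in-clinic dosing, Protocol 8.6 states: "The first dose of study drug for each patient will be administered and observed at the clinical study site at the Baseline visit". Under Protocol 4.1 a second dose depends on the investigator's opinion that "the patient had tolerability issues during the first dose administration, a second dose, at least 4 hours later, will also be observed". On rescue, the same section says: "Patients who experience cough that limits their ability to complete dosing will be given" salbutamol so that they can finish. Protocol 8.6 and SAP 3.7 repeat the rule without limiting it to a second dose, and the Baseline visit list in Protocol 6.2.2 expressly allows salbutamol while the initial dose is being taken.

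SAP 7.5 then lists the Baseline summaries. Interruptions: "The number of patients with study drug inhalations interrupted will be summarized for each dose (first dose only if only 1 dose was received", or both doses if two were taken. Salbutamol as pre-treatment: "The number of patients with physician-prescribed salbutamol taken prior to the dose will be summarized for each dose". Salbutamol used to carry on with an interrupted inhalation: "For patients with Inhalation interrupted during the second dose, the number of patients with salbutamol administered to continue dosing will be summarized". Only this last item leaves out the first dose. No reason is given, and SAP 12 does not mention the restriction.

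**The concern.** The first dose is the one that tests airway tolerance in every patient. Read literally, a patient who is stopped by cough on dose 1, is given salbutamol, finishes, and then takes dose 2 without interruption adds nothing to the rescue count. A near-zero row could be taken to mean that the first inhalation needed no rescue, although the row was never designed to show that.

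Two uses of the data are affected. First, the arms inhale different volumes (4 mL and 8 mL, Protocol 8.1), and comparing their safety is a stated objective, so rescue by arm is worth seeing. Second, the change from pre-dose to post-dose FEV1 after the initial dose is a named safety endpoint (Protocol 3.1, SAP 4.4), measured no later than 10 minutes after dosing ends. In a patient rescued mid-dose, that reading follows a beta-2 agonist, which can mask a fall. SAP 10.6 does not separate these patients.

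**Working it through.** The plan gives no figure for rescue, so the main check compares the places where first-dose rescue could be reported.

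| Planned output | Covers dose 1? | Shows salbutamol used to finish dose 1? |
|---|---|---|
| SAP 7.5, inhalation interrupted | Yes | No, interruption only |
| SAP 7.5, salbutamol before the dose | Yes | No, pre-treatment only |
| SAP 7.5, salbutamol to continue | No, second dose only | No |
| SAP 7.5, second in-clinic dose required | Indirectly | No |
| SAP 10.6, FEV1 fall of 15% or more | Yes | No; salbutamol appears only for symptomatic patients with that fall who were re-dosed |
| SAP 6.6 and 10.1, tolerability summary | Yes | No; cough and bronchospasm |
| SAP 7.6, concomitant medication table | Possibly | No; ATC class, without dose, timing or reason |
| SAP 7.5 and 7.6, listings | Possibly | Listed, not counted |

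No planned table isolates the item.

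**Where the in-clinic exposure lies.** The chance of at least one event in n doses at rate p is 1 − (1 − p)^n. At n = 50 and p = 1%, 5% and 10%, this gives 0.395, 0.923 and 0.995, matching SAP Table 1. The documents do not say how many patients take a second in-clinic dose. Assume 10% to 20% of an arm, that is 5 to 10 patients, with the same rescue rate at each dose:

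| Rate | 50 first doses | 5 second doses | 10 second doses |
|---|---|---|---|
| 5% | 0.923 | 0.226 | 0.401 |
| 10% | 0.995 | 0.410 | 0.651 |

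On that assumption first doses make up 50/60 = 83% to 50/55 = 91% of in-clinic inhalations. The equal rate is only for illustration: second-dose takers are selected for intolerance, but may also have been pre-treated.

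**How many patients might be affected.** Protocol Table 3 shows related cough in 1 + 1 + 3 + 1 + 1 + 1 = 8 of 36 AP01-dosed subjects (22%): 1 of 6 at 25 mg, 1 of 6 at 50 mg and 6 of 24 at 100 mg. Protocol 1.2.3 reports that cough kept none of them from taking the full dose. With zero events in n subjects, the one-sided 95% upper bound is 1 − 0.05^(1/n):

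- All AP01-dosed subjects: 1 − 0.05^(1/36) = 0.080. Times 50, that is 4 patients, so 0 to 4 per arm.
- IPF cohort alone: 1 − 0.05^(1/6) = 0.393, or about 39%.

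**The case against.** The strongest reply is that little is lost. A patient rescued on dose 1 is already counted as interrupted on dose 1. If re-dosed, the patient is counted as needing a second dose and, where salbutamol was newly added, as pre-treated because of intolerance. Actual dose, nebulization time and FEV1 falls are summarized for each dose, and cough and bronchospasm by arm. Rescue salbutamol is not a listed safety endpoint, and the affected item is one descriptive row under drug exposure. All of this stands, and it limits the point to a single missing attribute.

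A reader might go further and infer that first-dose intolerance goes unreported. The documents do not support that, for the reasons just given, and rescue may also appear in the listings.

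A reader might also take the 22% cough rate, assume that some share of coughers needed rescue, and predict several missed patients per arm. Protocol 1.2.3 contradicts that step: cough did not stop full dosing in any AP01-001 subject. The 22% also pools three dose levels. In the other direction, Protocol 1.2.3 does not say that no bronchodilator was used, and six IPF patients cannot rule rescue out.

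Calling rescue the most direct measure of tolerance would be opinion; SAP 3.1 names adverse events and post-dose spirometry.

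**Conclusion.** The gap is real but narrow. SAP 7.5 has no dedicated count of salbutamol given to complete an interrupted first dose, and no other planned table supplies one. The missing information is whether salbutamol was needed to finish dose 1, by arm. It alters no estimate or decision rule, but it helps in reading first-dose tolerability and the post-dose FEV1.

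The number affected is unknown and may be zero. The bound of 0 to 4 per arm assumes that AP01-001, a single-dose study mainly in volunteers, carries over to these patients, and that failure to take the full dose stands in for needing rescue. The IPF data alone allow a rate up to about 39%. The conclusion that the count is missing rests on the text and not on these figures.

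**What to change.** Replace the SAP 7.5 item with wording to this effect: *for each in-clinic dose (the first, and the second where received), report by treatment group the number and percentage of patients whose inhalation was interrupted and who were given salbutamol to go on, out of all patients who received that dose.* In SAP 10.6, flag the patients rescued during the first dose, so that their post-dose FEV1 can be read accordingly.

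The cost is one more table row and a flag. The sponsor must first confirm that first-dose rescue can be taken from the administration or concomitant medication eCRF. Protocol 7.4.4 requires concomitant medications to be recorded, but the documents show no dedicated field for this event, and its timing may have to be derived. No clinical rule changes.
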